	i. Relationship to Study Intervention	20
	ii. Expectedness	20
	iii. Severity	21
e. Re	porting Procedures	21
12. Data & Sa	fety Monitoring Plan	22
	agement	
14. Privacy, D	ata Storage & Confidentiality	27
16. Reference	s	31
17. Appendice	s	34
a. Ap	pendix 1: Study Workflow	34
b. Ap	pendix 2: Acute and Chronic Palliative Care Triggers	36
	pendix 3: Schedule of Events	
d. Ap	pendix 4: Survey Timelines and Rules	39
e. Ap	pendix 5: Data Collection and Timing	40
f. Ap	pendix 6: Adverse and Serious Adverse Event Reporting Diagram	41
	nendix 7: Study Contact Information	42

Protocol Version: 5.1 Dated: 13 June 2022 Page **3** of **42**

Abbreviations and Definitions

- Adverse Event (AE)
 - Any untoward medical occurrence associated with or observed in the context of a study procedure. For this study and patient population, an AE will be considered any suicidal ideation. No other events will be considered AEs as this patient population is ill and it is expected that other untoward medical occurrences will occur.
- Clinical Trial Management System (CTMS)
 - For this study, a CTMS known as OnCore will be utilized to manage the study's administrative responsibilities and subject level documentation.
- Duke Raleigh Hospital (DRaH)
 - o Study site in which eligible patients will be enrolled.
- Duke Regional Hospital (DRH)
 - Study site in which eligible patients will be enrolled.
- Duke University Hospital (DUH)
 - Study site in which eligible patients will be enrolled.
- Electronic Data Capture (EDC)
 - For this study, the EDC will be REDCap, which is a secure, Duke approved EDC platform in which relevant study data, such as screening, enrollment, and clinical variables will be documented.
- Electronic Health Record (EHR)
 - Used interchangeably with EMR; the EHR is the patient-specific medical record located in the secure MaestroCare (aka: EPIC).
- Electronic Medical Record (EMR)
 - Used interchangeably with EHR; the EMR is the patient-specific medical record located in the secure MaestroCare (aka: EPIC).
- Electronic Patient Reported Outcomes (ePRO)
 - ePRO can be used to describe study source, such as the patient-completed surveys (e.g., PTSS), or can refer to the system that houses patient-derived data. For this study, ePRO may refer to the surveys OR it may refer to the system which houses the patient-derived data, which is the web application known as "PCplanner."
- General Anxiety Disorder-7 (GAD-7)
 - Anxiety symptoms
- Intensive Care Unit (ICU)

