 - o Defined as any medical, surgical, trauma, neurological, cardiac, or cardio-thoracic unit in which a patient is receiving cardiac or respiratory support for survival means.
- Institutional Review Board (IRB)
 - Ethical and regulatory committee who provides approval and oversight of clinical trial at study site.
- Manual of Operating Procedures (MOP)
 - A document detailing instructions for a specific task or set of tasks; often used to ensure consistency and accuracy among the study team.
- National Institute of Aging (NIA)
 - Study Sponsor, branch of the National Institute of Health (NIH)
- NEST (Needs at the End of life Screening Tool)
 - Needs assessment.
- PCplanner
 - A novel web application developed by DHTS and external vendor, One Cow Standing, LLC (Durham, NC) that interfaces with the EMR on a daily basis, pulling relevant clinical data from patients admitted to an ICU setting that meet general study criteria. The web

Protocol Version: 5.1 Dated: 13 June 2022 Page 4 of 42

application serves as the technological platform by which the study is to be conducted and the primary data (e.g., surveys) are completed by enrolled subjects.

- Patient Health Questionnaire-9 (PHQ-9)
 - o Depression symptoms
- Post-Traumatic Stress Scale survey (PTSS)
 - o PTSD symptoms
- Protocol Deviation (PD)
 - An inadvertent event or event this is out of the control of the study team and/or the subject that occurs outside of the study protocol design and/or procedures.
- Protocol Violation
 - An act of intentionality that is committed by the study team and/or the subject that occurs outside of the study protocol design and/or procedures.
- System Usability Scale (SUS)
 - Usability scale used to measure usability of web-application.
- Serious Adverse Event (SAE)
 - Defined as an adverse event that is both serious and expected in nature; the event may have a reasonable possibility that it is related to a study. SAEs for this study are defined as a suicide attempt, a hospitalization, or death.
- Suicide Ideation (SI)
 - The idea of committing self-harm and/or the intent to act on the idea of committing self-harm.
- Unanticipated Problem (UP)
 - Any other event, not meeting the definition of PD, UP, AE or SAE that, in the opinion of the principal investigator, merits documentation as it occurred outside the expected design of the study and/or study procedures. These events, like PDs, UPs, AEs, or SAEs, may be reported to the IRB and/or the study sponsor, as applicable.

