Adverse events (AEs) generally would include extremely high distress levels (PHQ-9 score >25, GAD-7 score >20, PTSS score >34) or active suicidal ideation (i.e., endorsement of PHQ-9 suicidal ideation item plus a positive response to a branching logic item signifying active planning that would follow inquiring about a plan). A serious adverse event (SAE) would be a suicide attempt, a hospitalization, or death.

It is anticipated, in this study, for AEs to be extremely uncommon as it is a behavioral study. However, it is possible that participants could exhibit signs of and/or experience suicidal ideations with intent or thoughts of intent to act on such ideations. No other event, outside of suicidal ideation with intent or thoughts of intent to act on ideations will be considered an AE for this trial.

Like, AEs, it is not anticipated that SAEs will occur. However, for this study, an SAE would include a suicide attempt, a hospitalization (of family member), or death (of family member). All serious adverse events will be reported within the standard timelines required to the IRB, study sponsor, and/or DSMB, as appropriate and when applicable.

Protocol Deviations (PDs) and Unanticipated Problems (UPs)

Protocol deviations are errors made by study staff or deviations from plan made by study clinicians such as failure to conduct a family meeting. Unanticipated problems could consist of issues such as failure of the study staff to respond in a timely manner to suicidal ideation reported by a participant.

Given the nature of this study, it is anticipated that most enrolled family members will not complete their study surveys within the assigned protocol window. Additionally, it is expected that surveys may be missed as these are self-reported outcomes. As such, these will not be considered protocol deviations. Should other protocol deviations or unanticipated problems occur, they will be discussed with the PI, documented, and reported to the IRB, study sponsor, and/or DSMB, as appropriate and when applicable.

Period and Frequency for Event Assessment and Follow-Up

Protocol deviations and other unanticipated problems, as well as AEs and SAEs, will be recorded in the data collection system throughout the study.

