The study team will record all reportable events with start dates occurring any time after informed consent is obtained until 7 days after the last day of study participation. At each study survey, the study team will inquire by way of verbal or written request and/or EMR review, of the occurrence of AE/SAEs since the last survey. Events will be followed for outcome information until resolution or stabilization.

Characteristics of an Adverse or Serious Adverse Event Relationship to Study Intervention

To assess relationship of an event to study intervention, the following guidelines are used:

• **Definitely Related**: The definition of an AE/SAE that is definitely related would include episodic distress triggered by either a study survey or some study material (e.g., a video).

Protocol Version: 5.1 Dated: 13 June 2022 Page **20** of **42**

- Possibly Related: The definition of an AE/SAE that is possibly related would include simply
 experiencing high levels of distress during the trial period. That is, this could follow a
 reasonable temporal sequence from administration of the study intervention, but that could
 readily have been produced by a number of other factors.
- **Not Related**: An AE/SAE that is not related would include a hospitalization for a car accident, etc. That is, it would be an adverse event that is clearly not related to the investigational agent/procedure i.e. another cause of the event is most plausible; and/or a clinically plausible temporal sequence is inconsistent with the onset of the event and the study intervention and/or a causal relationship is considered biologically implausible.

Expectedness

- **Unexpected** The definition of an unexpected AE/SAE will be one whose nature or severity of the event is not consistent with information about the condition under study or intervention in the protocol, consent form, product brochure, or investigator brochure.
- **Expected** There are no events known to be associated with the intervention. Psychological distress is expected given the severity of patients' illnesses and their family members' involvement in decision making about a life-threatening illness.

Severity

The following scale will be used to grade adverse events:

- 1. Mild: no intervention required; no impact on activities of daily living (ADL). For example, elevated distress levels (e.g., PHQ-9 score >25, GAD-7 score >20, PTSS score >34).

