- 2. Moderate: minimal, local, or non-invasive intervention indicated; moderate impact on ADL. For example, suicidal ideation endorsed (i.e., PHQ-9 item #9), though no plan endorsed.
- 3. Severe: significant symptoms requiring invasive intervention; subject seeks medical attention, needs major assistance with ADL. For example, suicide attempt, hospitalization due to distress symptoms, or death.

Reporting Procedures

Adverse and Serious Adverse Events

We have a strong plan for AE/SAE reporting and follow up. First, we have a very robust monitoring system for psychiatric and emotional symptoms. We will know 'alert' values of depression, anxiety, and PTSD symptoms the second a questionnaire is completed via the mobile app. For symptoms that are either great in total burden (i.e., total score is high), we will call the participant to check in. For specific symptoms such as the suicidal ideation item in the PHQ-9 depression questionnaire, we will also call the participant and assess the severity of the situation, triaging them as appropriate to psychiatric support. Last, we have broadly placed our email addresses and phone numbers in all study materials and will encourage people to contact us regarding any issues.

Since this is a psychosocial intervention, we do not expect study related physical issues to occur. Furthermore, there is no lab work involved.

All deaths will be reported to NIA Program Officer, the DSMB Chair, and the central IRB within 72 hours of study's knowledge of death. For each patient who dies, a brief report containing the following variables will be provided:

Age
Principal diagnosis
Number of comorbidities
Admission APACHE II score
Days since enrollment

Protocol Version: 5.1 Dated: 13 June 2022 Page 21 of 42

Brief description of circumstances surrounding death including expected or unexpected.

All **adverse events that are both serious** (SAE) **and unexpected** (i.e., have not been previously reported for the study's intervention) will be reported to the IRB, NIA PO, and to the independent data and safety monitoring body according to the timeframe displayed in appendix 6. The summary of all other SAEs should be reported to NIA PO and to the DSMB or a Safety Officer, if either is appointed, quarterly, unless otherwise requested by the DSMB or a Safety Officer.

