Serious (fatal or life-threatening) SAEs that are unanticipated (i.e., not listed in the Data and Safety Monitoring Plan) and that are related to the intervention will be reported to the NIH Program Officer and to the DSMB Chair according to the timeframe displayed in appendix 6.

The summary of all other SAEs will be reported to NIH Program Officer and to the DSMB quarterly, unless otherwise requested by the DSMB. Additionally, for SAEs, we will hold an all-investigator

teleconference within 7 days. The PIs will draft a description of the SAE and an action plan. This will be passed on to the IRB, the NIH, and DSMB within 72 hours of the teleconference. See appendix 6 for identifying and reporting structure.

Protocol Deviations and Other Unanticipated Problem Reporting

Incidents or events that meet the reporting criteria, as outlined by the Duke IRB, will be reported to the Duke IRB as needed.

The following will be included, at a minimum:

Table	
Information	Timing
Study operations: Enrollment rate,	Reviewed on a weekly basis
refusals, dropouts	
Intervention adherence: Total app logins, number of pages viewed per use, surveys completed, total time	Numerous dimensions via software analytics
spent per login	
Distress:	
-Suicidal ideation	-Real-time monitoring with automated email alert sent to all study staff if suicidal ideation present
-Psychological distress symptoms	-Every 6 months by DSMB and every year by IRB
Unanticipated Problems, Adverse	Reviewed by PI and study staff
Events, and Serious Adverse	immediately on discovery.
Events: hospitalizations, life-	•
threatening events, death	

- A detailed description of the event, incident, experience, or outcome;
- A description of any changes to the protocol or other corrective actions that have been taken or are proposed in response to the unanticipated problem.

12. Data & Safety Monitoring Plan

Overall framework for safety monitoring and what information will be monitored

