Study Report Outline for the Independent Monitors(s) (Interim or Annual Reports)

The study team will generate Study Reports for the Independent Monitor and will provide information on the following study parameters: NEST, PHQ-9, GAD-7, and PTSS scores; enrollment success; rate of consent; rate of successful randomization; retention rates; and AE/SAEs. Study Report tables will be generated only from aggregate (not by group assignment) baseline and aggregate safety data for the study population.

Submission of On-Site Monitoring/Audit and Inspection Reports

The IRB, IMC, and NIA Program Officials will receive copies of all study monitoring/audit or inspection reports within 14 day of PI receipt.

Table A

Data type	Frequency of review	Reviewer
Subject accrual (including compliance with protocol enrollment criteria)	Monthly	PI, Internal QA Reviewer
	Semi-annually	Independent Monitor(s)
Status of all enrolled subjects, as of	Monthly	PI, Internal QA Reviewer
date of reporting	Semi-annually	Independent Monitor(s)
Data entry quality control checks on 5% of charts	Weekly	QA Reviewer
Adherence data regarding study visits	Monthly	Pls, Internal QA Reviewer
and intervention	Semi-annually	Independent Monitor(s)
AEs and rates (including out-of-range	Monthly	Pls, Internal QA Reviewer
lab values)	Semi-annually	Independent Monitor(s)
	Annually	NIA FDA (If Applicable)
SAEs (unexpected and related)	Per occurrence	Pls, Independent Monitor (s) NIA, FDA (if applicable)
SAEs (expected or unrelated)	Per Occurrence	Pls, Internal QA Reviewer
	Annually	Independent Monitor (s), NIH/NIA
Unanticipated Problems	Monthly	Pls, Internal QA Reviewer
	Per Policy	IRB, FDA (if applicable)

Data management plan

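### The protocol gives conflicting rules for what counts as an adverse event, a glossary SAE entry at odds with Section 11, and two intervals for SAE summaries

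*Combined protocol and SAP*

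**What the plan says.** Four places state or imply what an AE is.

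- **Abbreviations and Definitions**, Adverse Event entry: "an AE will be considered any suicidal ideation". It adds that nothing else counts.
- **Section 11, Adverse Events and Serious Adverse Events, first paragraph**: "Adverse events (AEs) generally would include extremely high distress levels (PHQ-9 score >25, GAD-7 score >20, PTSS score >34"), or ideation on the PHQ-9 item together with a positive answer to the follow-up item about a plan.
- **Same subsection, second paragraph**: "No other event, outside of suicidal ideation with intent or thoughts of intent to act on ideations will be considered an AE".
- **Section 11, Severity**: the mild example is "elevated distress levels (e.g., PHQ-9 score >25, GAD-7 score >20, PTSS score >34"), and the moderate example is "suicidal ideation endorsed (i.e., PHQ-9 item #9), though no plan endorsed".

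Two passages use the term in further ways. The opening of Section 11 limits AEs and SAEs to events affecting the family member. Yet the possible stopping plan in Section 12 (Data Safety Monitoring Board) makes three-month mortality the primary adverse event for patients, and PHQ-9 and PTSS symptoms the primary adverse event for caregivers.

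For SAEs, the glossary entry reads "Defined as an adverse event that is both serious and expected in nature". Section 11 lists a suicide attempt, hospitalization or death of the family member and sets no condition on expectedness. Reporting Procedures sends events that are serious and unexpected to expedited reporting. For the remainder, it says "The summary of all other SAEs will be reported to NIH Program Officer and to the DSMB quarterly", unless the DSMB asks otherwise. In Section 12, Table A has a row "SAEs (expected or unrelated") that goes annually to the Independent Monitor(s) and NIH/NIA.

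**The concern.** Two of the four AE rules, the glossary and the second paragraph of Section 11, are exclusive: each says that nothing else counts. They cannot be read as layers of one definition. The mild and moderate grades then apply to events that the second paragraph says are not AEs.

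This affects operative safety rules. Section 12 names AE reports and the PHQ-9 ideation item as the DSMB's primary safety measures. It allows formal tests of AE rates between groups at the DSMB's request, and it requires the Annual Report to judge whether AE rates match pre-study assumptions. A rate has no fixed meaning until one rule decides which events enter it. If staff apply different rules at different times or sites, a difference between groups, or its absence, could reflect labelling.

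The SAE wording raises a similar problem on a smaller scale. The glossary and the reporting rules pull in opposite directions on expectedness, and two intervals are given for overlapping sets of events.

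**Working it through.** The plan states no figure to reproduce, so the check is a side-by-side classification.

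**AE rules.** Each caregiver event is classified under the literal wording. An active plan is taken to imply intent or thoughts of intent. Scores are at or below the cut-offs in the second and third rows.

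| Caregiver event | Glossary | §11, para 1 | §11, para 2 | Severity scale |
|---|---|---|---|---|
| Distress score above cut-off, no ideation | no | yes | no | yes (mild) |
| Ideation, no intent or plan | yes | no | no | yes (moderate) |
| Ideation with intent, no plan | yes | no | yes | yes (moderate) |
| Ideation with active plan | yes | yes | yes | yes (no example grade) |
| Attempt, distress-related hospitalization, or death | no | no | no | yes (severe) |

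The last row matters least, because Section 11 handles those events as SAEs. Leaving it out, all six pairs of rules still disagree:

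- glossary and para 1: rows 1, 2 and 3
- glossary and para 2: row 2
- glossary and Severity: row 1
- para 1 and para 2: rows 1 and 3
- para 1 and Severity: rows 2 and 3
- para 2 and Severity: rows 1 and 2

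The four rules agree on one caregiver event only, ideation with an active plan, and the Severity scale gives no example grade for it. Section 11's relatedness guidance also treats high distress alone as a possibly related AE/SAE, which the second paragraph rules out.

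Patient death is an AE under none of the four rules, yet the possible stopping plan calls it the primary adverse event for patients.

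**SAE definition.** If every SAE is expected by definition, the serious-and-unexpected class has no members. The Expectedness text in Section 11 says that no events are known to be associated with the intervention and names only psychological distress as expected. An attempt, hospitalization or death could therefore hardly meet the glossary's condition, although the glossary entry itself lists those three events.

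**SAE interval.** An expected SAE falls within the quarterly summary in Reporting Procedures and within the annual row of Table A. Even if the DSMB and the Independent Monitor(s) are different bodies, the NIH/NIA is a recipient under both. Section 9 gives about 41 months of data collection:

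- quarterly: 41 / 3 = 13.7, so about 13 completed summaries
- annual: 41 / 12 = 3.4, so about 3

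**The case against.** The case on the other side has four parts.

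**The count of four may be generous.** The first paragraph says what AEs generally include, the second gives the rule for this trial, and the Severity entries are examples. Suppose the second paragraph governs. The glossary still counts ideation without intent, and the Severity scale still grades events that the governing rule excludes. The contradiction remains.

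**The DSMB charter may settle it.** Section 12 leaves adverse outcome definitions and the AE reporting protocol to a charter approved before enrollment. The charter is not among the documents, and the Appendix 6 diagram is not shown, so expedited time frames cannot be checked and are not counted as missing. This stands as a limit on the finding. A separate charter does not, however, correct the rules that Version 5.1 itself states.

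**Safeguards do not use the AE label.** This stands. Reported ideation triggers a real-time alert, high totals and the ideation item prompt a call, alert resolutions are logged for the DSMB, and deaths are reported within 72 hours. The DSMB also sees PHQ-9, GAD-7 and PTSS scores at each review. A reader might infer that events would go undetected or be lost; the documents do not show that.

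**The SAE point is narrower than it looks.** A reader might infer that SAEs are defined both as expected and as unexpected. They are not. Only the glossary puts expectedness into the definition. The serious-and-unexpected group is a subset for expedited reporting, and expedited alongside periodic reporting is ordinary tiering. The interval mismatch is administrative, and the quarterly default yields to a DSMB request, but Table A does not say that it reflects one.

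**Conclusion.** The concern holds as an internal contradiction in operative safety rules. The four AE rules disagree pairwise on caregiver events, so AE reports, AE rates and any comparison of them between groups depend on which text is followed. The other primary safety measure, PHQ-9 item 9, is unaffected. The risk shown is inconsistent classification and reporting. The primary endpoint, its analysis and the power calculation are not touched.

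The glossary's expectedness condition cannot be squared with Section 11. The quarterly and annual intervals conflict for overlapping events, at about 13 summaries against 3.

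No AE count by definition can be given. A reader might turn to the statement in Section 10 that under 5% of participants in similar studies needed a call. Applied to 150 caregivers this is 0.05 × 150 = 7.5, so at most 7. But it is an upper bound on calls in other studies, not an AE rate here. The accompanying remark that none needed acute psychiatric referral does not mean that none had ideation with intent. A contrast such as zero AEs under one rule and seven or more under another is therefore not supported.

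The conclusion rests on a literal reading of Version 5.1 and on the charter being unavailable.

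**What to change.** 1. Reconcile the glossary, both paragraphs of Section 11, the Severity scale and the wording of the possible stopping plan into one AE definition, chosen by the sponsor with the DSMB and consistent with the charter. No clinical threshold is proposed here. If the definition uses intent, it should say how intent is ascertained, since the survey's follow-up item is described as asking about a plan.
2. Whatever definition is chosen, tabulate separately for the DSMB, by masked arm: distress above the protocol's threshold, ideation without a plan, ideation with a plan, and attempt. The safety picture then does not hang on the label.
3. Remove the expectedness condition from the glossary SAE entry, so that it matches the SAE list and the reporting tiers in Section 11.
4. State one interval for summaries of other SAEs, the same in Reporting Procedures and Table A.

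The cost is a protocol clarification and one extra safety table. The distress scores and the ideation item with its plan follow-up are already collected, and attempts are already reportable as SAEs.
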